5.3 ASSESSMENT OF SAFETY

Safety will be assessed throughout the trial by AEs determined according to NCI CTCAE (Version 4.03).

5.3.1 Physical examination

A full physical exam must include: vital sign measurements, cardiopulmonary examination, examination of the regional lymph nodes, an examination of the abdomen and an assessment of the mental and neurological status. Additional symptoms which have not been reported during a previous examination must be clarified. Wherever possible the same investigator should perform this examination.

Measurement of height (in cm), body weight (in kg) and the evaluation of the performance score ECOG will be conducted at the times specified in the [Flow Chart](#).

5.3.2 Vital Signs

Vital sign measurements include blood pressure (systolic blood pressure, diastolic blood pressure), pulse rate, temperature.

5.3.3 Safety laboratory parameters

Safety lab will be performed locally at each participating site. Following parameters should be evaluated at each timepoint:

Table 5.3.3: 1 Safety laboratory parameters

Category	Parameters
Hematology	Red blood cell count (RBC), haemoglobin, haematocrit, platelet count, white blood cell count (WBC), with differential (neutrophils, lymphocytes, monocytes, eosinophils, basophils)
Coagulation	International Normalized Ratio (INR), activated Partial Thromboplastin Time (aPTT), Fibrinogen.
Chemistry	
Electrolytes	Sodium, potassium, calcium, magnesium, chloride, bicarbonate (HCO ₃)
Liver function tests	alkaline phosphatase, aspartate aminotransferase (AST), alanine aminotransferase (ALT), γ - glutamyltransferase (GGT), total bilirubin
Renal function parameters	Blood urea/blood urea nitrogen (BUN), creatinine; Creatinine clearance (see Appendix 10.2).
Other	glucose, albumin, cholesterol, triglycerides, phosphorus, lactate dehydrogenase (LDH), total protein, uric acid, creatine phosphokinase (CPK); in case of pathological CPK further evaluation (e.g by determination of isoenzymes, troponin assays, ECG exam) should be performed as clinically indicated
Urinalysis	pH, protein, glucose, ketones, blood, leucocytes, nitrite; in case of pathological finding further evaluation should be performed and results documented. Proteinuria per se will only result in treatment interruptions if associated to other renal pathology which would qualify for treatment interruption i.e. CTCAE \geq 3 AE, or decrease in renal clearance to $<$ 45 ml/min GFR
Pregnancy test	β -HCG testing in urine or serum in women of childbearing potential (WOCBP)

The investigator should complete additional evaluations of laboratory tests as clinically indicated.

5.3.4 Electrocardiogram

12-lead ECG will be taken at the time points specified in the [Flow Chart](#). The investigator will review the ECG recording, comment on any clinical significance and if applicable record any ECG abnormality that meets AE criteria.

5.3.5 Assessment of adverse events

5.3.5.1 Definitions of AEs

Adverse event

An adverse event (AE) is defined as any untoward medical occurrence in a patient or clinical investigation subject administered a medicinal product and which does not necessarily have to have a causal relationship with this treatment.

An AE can therefore be any unfavourable and unintended sign (including an abnormal laboratory finding), symptom, or disease temporally associated with the use of a medicinal product, whether or not considered related to the medicinal product.

Adverse reaction

An adverse reaction is defined as a response to a medicinal product which is noxious and unintended. Response in this context means that a causal relationship between a medicinal product and an adverse event is at least a reasonable possibility. Adverse reactions may arise from use of the product within or outside the terms of the marketing authorisation or from occupational exposure. Conditions of use outside the marketing authorization include offlabel use, overdose, misuse, abuse and medication errors.

Serious adverse event

A serious adverse event (SAE) is defined as any AE which:

- results in death,
- is life-threatening,
- requires inpatient hospitalisation or prolongation of existing hospitalisation,
- results in persistent or significant disability or incapacity,
- is a congenital anomaly/birth defect, or
- is to be deemed serious for any other reason if it is an important medical event when based upon appropriate medical judgment which may jeopardize the patient and may require medical or surgical intervention to prevent one of the other outcomes listed in the above definitions.

Life-threatening in this context refers to an event in which the patient was at risk of death at the time of the event; it does not refer to an event that hypothetically might have caused death if more severe.

If cancer is the indication for treatment, only cancers of new histology qualify as a serious event. Every new occurrence of cancer must be reported as a serious event regardless of the duration between discontinuation of the drug and the occurrence of the cancer.

AEs considered “Always Serious”

In accordance with the European Medicines Agency initiative on Important Medical Events, Boehringer Ingelheim has set up a list of AEs, which by their nature, can always be considered to be “serious” even though they may not have met the criteria of an SAE as given above.

The latest list of “Always Serious AEs” can be found in the RDC. These events should always be reported as SAEs as described in [Section 5.3.6](#).

Adverse events of special interest (AESIs)

The term AESI relates to any specific AE that has been identified at the project level as being of particular concern for prospective safety monitoring and safety assessment within this trial, e.g. the potential for AEs based on knowledge from other compounds in the same class. AESI need to be reported to the Sponsor’s Pharmacovigilance Department within the same timeframe that applies to SAE, see [Section 5.3.6](#).

The following are considered as AESIs:

Hepatic injury

A hepatic injury is defined by the following alterations of hepatic laboratory parameters:

- For patients with normal liver function at baseline (ALT, AST, and bilirubin within normal limits at baseline):
 - an elevation of AST and/or ALT ≥ 3 fold ULN combined with an elevation of total bilirubin ≥ 2 fold ULN measured in the same blood draw sample, and/or
 - Marked peak aminotransferase (ALT, and/or AST) elevations ≥ 10 fold ULN
- For patients with abnormal liver function at baseline (AST and/or ALT > ULN)
 - an elevation of AST and/or ALT ≥ 5 fold ULN combined with an elevation of total bilirubin ≥ 2 fold ULN measured in the same blood draw sample, with the exclusion of the causes due to underlying diseases.

These lab findings constitute a hepatic injury alert and the patients showing these lab abnormalities need to be followed up according to the “DILI checklist” provided via the RDC system. In case of clinical symptoms of hepatic injury (icterus, unexplained encephalopathy, unexplained coagulopathy, right upper quadrant abdominal pain, etc.) without lab results (ALT, AST, total bilirubin) available, the investigator should make sure these parameters are analysed, if necessary in an unscheduled blood test. Should the results meet the criteria of hepatic injury alert, the procedures described in the DILI checklist should be followed.

Intensity of AEs

The intensity of adverse events should be classified and recorded according to the Common Terminology Criteria for Adverse Events (CTCAE) version 4.03 in the (e)CRF.

Causal relationship of AEs

The definition of an adverse reaction implies at least a reasonable possibility of a causal relationship between a suspected medicinal product and an adverse event. An adverse reaction, in contrast to an adverse event, is characterised by the fact that a causal relationship between a medicinal product and an occurrence is suspected.

Medical judgment should be used to determine the relationship, considering all relevant factors, including pattern of reaction, temporal relationship, de-challenge or re-challenge, confounding factors such as concomitant medication, concomitant diseases and relevant history.

Arguments that may suggest that there is a reasonable possibility of a causal relationship could be:

- The event is consistent with the known pharmacology of the drug
- The event is known to be caused by or attributed to the drug class.
- A plausible time to onset of the event relative to the time of drug exposure.
- Evidence that the event is reproducible when the drug is re-introduced
- No medically sound alternative aetiologies that could explain the event (e.g. pre-existing or concomitant diseases, or co-medications).
- The event is typically drug-related and infrequent in the general population not exposed to drugs (e.g. Stevens-Johnson syndrome).
- An indication of dose-response (i.e. greater effect size if the dose is increased, smaller effect size if dose is diminished).

Arguments that may suggest that there is no reasonable possibility of a causal relationship could be:

- No plausible time to onset of the event relative to the time of drug exposure is evident (e.g. pre-treatment cases, diagnosis of cancer or chronic disease within days / weeks of drug administration; an allergic reaction weeks after discontinuation of the drug concerned)
- Continuation of the event despite the withdrawal of the medication, taking into account the pharmacological properties of the compound (e.g. after 5 half-lives).

Of note, this criterion may not be applicable to events whose time course is prolonged despite removing the original trigger.

- Additional arguments amongst those stated before, like alternative explanation (e.g. situations where other drugs or underlying diseases appear to provide a more likely explanation for the observed event than the drug concerned).
- Disappearance of the event even though the study drug treatment continues or remains unchanged.

[figure not shown]

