3.3.2 Inclusion criteria

1. Adult patients ≥ 18 years old
2. Patients must have histologically confirmed urothelial tract carcinoma. Patients with urothelial carcinoma of the bladder, upper tract or urethra are eligible.
3. Locally advanced or metastatic urothelial tract carcinoma that is not amenable to surgical treatment.
4. Progressive disease on or after platinum-containing regimen and is not a candidate for another platinum therapy. Following cases will be considered as one line of chemo:
 - Patients receiving platinum-based regimen in the peri-operative setting and subsequently in the metastatic setting
 - Patients who are not refractory to platinum based chemotherapy after one line in metastatic setting (defined as more than 6 months without clinical or radiological PD after the end of first line platinum based chemotherapy) and subsequently receive another line of platinum based chemotherapy in metastatic setting
5. Received no more than one line of prior systemic chemotherapy for recurrent/metastatic disease, and this previous chemotherapy should be platinum based (immunotherapy is not considered as a systemic chemotherapy). If platinum based chemotherapy was administered in the peri-operative setting, patient should have progressed during or within 12 months after treatment .
6. Measurable disease according to RECIST 1.1.
7. ECOG performance status 0 or 1
8. Life expectancy of at least 3 months (12 weeks)
9. Archival tissue biopsies (blocks) available for biomarker testing at pre-screening and for tissue banking for a potential bridging study for CDx (for details refer to [Section 5.5](#)).
10. Patients should complete a pre-screening biomarker analysis and should fulfill the following:
 - Cohort A: Tumour with a ERBB2 or ERBB3 mutation, or ERBB2 gene amplification (for definitions please refer to [section 5.5.1](#))
 - Cohort B: Tumour with EGFR amplification (for definitions please refer to [section 5.5.1](#))
11. Adequate organ function, defined as all of the following:
 - a. Absolute neutrophil count (ANC) $\geq 1500 / \text{mm}^3$.
 - b. Platelet count $\geq 75,000 / \text{mm}^3$.

- c. Estimated creatinine clearance > 45 ml / min. Refer to [Appendix 10.2](#).
 - d. Total Bilirubin ≤ 1.5 times upper limit of (institutional/central) normal (Patients with Gilbert's syndrome total bilirubin must be ≤ 4 times institutional upper limit of normal).

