 - e. Aspartate amino transferase (AST) or alanine amino transferase (ALT) \leq three times the upper limit of (institutional/central) normal (ULN) (if related to liver metastases \leq five times ULN).
12. Recovered from any previous therapy related toxicity to \leq Grade 1 at study entry (except for stable sensory neuropathy \leq Grade 2 and alopecia)
 13. Written informed consent for pre-screening that is consistent with ICH-GCP guidelines for tissue, blood, urine collecting and biomarker assessment to confirm eligibility for enrollment into pre-screening phase.
 14. Written informed consent that is consistent with ICH-GCP guidelines to confirm eligibility for enrollment into the trial once pre-screening was successfully completed.

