10.4 APPENDIX 4: CLINICAL EVALUATION OF LIVER INJURY

10.4.1 Introduction

Alterations of liver laboratory parameters, as described in [Section 5.3.5.1](#) (Adverse Events of Special Interest), are to be further evaluated using the following procedures:

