10.4.2 Procedures

Any elevation of ALT/AST and bilirubin qualifying as laboratory alert should be confirmed using the initial sample if possible.

If the alert is confirmed on initial sample, or it is not possible to repeat testing using initial sample, the following must be completed;

- 1) Evaluate the patient within 48 hours and,
- 2) Perform the following laboratory tests:
 1. Repeat of AST, ALT, bilirubin (with fractionation to total and direct)
 2. Complete blood count and cell morphology
 3. Reticulocyte count
 4. CK

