Thrombocytes, eosinophils
*If clinically indicated (e.g immunocompromised patients)

Long term follow-up

- Initiate close observation of subjects by repeat testing of ALT, AST, and bilirubin (with fractionation to total and direct) at least weekly until the laboratory ALT and or AST abnormalities stabilize or return to normal, then according to the protocol. Depending on further laboratory changes, additional parameters identified e.g. by reflex testing will be followed up based on medical judgement and Good Clinical Practices (GCP).

Report any resulting diagnoses via the eCRF.

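### The isolated ALT/AST ≥ 10 × ULN hepatic-injury alert covers only patients with normal ALT, AST and bilirubin at baseline; extend it to all patients

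*Protocol*

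**What the plan says.** Section 5.3.5.1 of the protocol lists hepatic injury as an AESI and sets laboratory criteria for two baseline groups.

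- The first group has "normal liver function at baseline (ALT, AST, and bilirubin within normal limits at baseline". It has two limbs: AST and/or ALT ≥ 3 × ULN with total bilirubin ≥ 2 × ULN in the same sample, and/or "Marked peak aminotransferase (ALT, and/or AST) elevations" of ≥ 10 × ULN, with no bilirubin condition.
- The second group opens "For patients with abnormal liver function at baseline (AST and/or ALT > ULN". It has one limb: AST and/or ALT ≥ 5 × ULN with total bilirubin ≥ 2 × ULN in the same sample, leaving out rises explained by underlying disease.

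Section 3.3.2 allows entry above ULN. Criterion 11e accepts AST or ALT up to 3 × ULN, or 5 × ULN "if related to liver metastases". Criterion 11d accepts total bilirubin up to "1.5 times upper limit of (institutional/central) normal", or 4 × ULN with Gilbert's syndrome.

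Meeting a criterion starts the 24-hour report (Section 5.3.6) and the work-up in Appendix 10.4. That appendix covers "Alterations of liver laboratory parameters, as described in" Section 5.3.5.1. Once an alert is confirmed, or the first sample cannot be retested, the site must "Evaluate the patient within 48 hours". Imaging and the DILI checklist follow as needed, with repeat tests "at least weekly until the laboratory ALT and or AST abnormalities stabilize or return to normal".

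**The concern.** The combined limb adapts to a raised baseline: its aminotransferase threshold moves from 3 to 5 × ULN. The isolated limb does not adapt; it disappears, and the protocol gives no reason. As a result, a patient known to have raised enzymes at entry has a weaker automatic trigger than a patient with normal values.

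Liver metastases do not explain the difference. Criterion 11e admits patients up to 3 × ULN without them, and the abnormal-baseline limb already carries an exclusion for underlying disease.

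At stake is the prompt, rule-based handling of a marked isolated rise. Section 2.3 reports hepatic failure, including deaths, in under 1% of afatinib patients, and commits the trial to finding and following up liver laboratory changes in good time.

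**Working it through.** No sample size, error rate or event count bears on this point, and the plan gives no figure to reproduce. The check is to read Section 5.3.5.1 as a decision table and then look for any other route to the alert.

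**Decision table**

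| Baseline | On-treatment ALT/AST | Bilirubin | Alert? |
|---|---|---|---|
| All three normal | ≥ 3 × ULN | ≥ 2 × ULN, same sample | Yes |
| All three normal | ≥ 10 × ULN | Any | Yes |
| AST and/or ALT > ULN | ≥ 5 × ULN | ≥ 2 × ULN, same sample, underlying-disease causes excluded | Yes |
| AST and/or ALT > ULN | 10, 15 or 20 × ULN | < 2 × ULN | No, at any height |
| Bilirubin > ULN, AST and ALT normal | Any | Any | No criterion assigned |

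**Two patients with the same peak.** Both peak at 15 × ULN with bilirubin below 2 × ULN. The one who entered with all three values normal triggers an alert. The one who entered at 1.1 × ULN has reached 15 / 1.1 = 13.6 times baseline and triggers none.

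**Other routes to the alert**

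- Appendix 10.4.1 refers back to Section 5.3.5.1, and 10.4.2 acts only on values that already qualify. Neither adds a threshold.
- The clause in 5.3.5.1 on clinical symptoms of liver injury asks for the tests to be done, but the checklist follows only if the results meet the same criteria.
- SAP Sections 7.8.1 and 7.8.2 list hepatic events by MedDRA groupings and tabulate enzyme elevations. These are analyses, not real-time alerts.

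**What 10 × ULN means relative to entry**

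- Entry at 1.1 × ULN: 10 / 1.1 = 9.1 times baseline.
- Entry at 3 × ULN (the 11e limit): 10 / 3 = 3.3 times.
- Entry at 5 × ULN (the 11e limit with liver metastases): 10 / 5 = 2.0 times.

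**Timing with and without an alert**

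- With an alert: evaluation within 48 hours, then repeat tests at intervals of at most 7 days.
- Without an alert, but with a drug-related AE of grade ≥ 3: treatment pauses (Table 4.1.4.1.1:1) and stops if there is no recovery within 14 days, unless the sponsor's monitor and the investigator agree otherwise.
- Without either: the flow chart schedules safety laboratory tests on course 1 day 1, course 1 day 8 and day 1 of each later 28-day course. The nominal gaps are 8 − 1 = 7 days, 29 − 8 = 21 days, then 28 days (24 to 32 with the ± 2-day window at both visits). These are scheduled intervals only; unscheduled tests are allowed at any time.

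**The case against.** The best counter-argument is that the protocol has other safeguards and that the omission may be deliberate.

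**Safeguards.** Section 5.3.3 tells the investigator to add laboratory tests when clinically indicated, and Section 6.1 allows extra visits. Section 5.3.6 requires clinically relevant laboratory changes to be recorded as AEs and followed until resolved or sufficiently characterized. Section 5.3.5.1 lets an important medical event be classed as serious on medical judgement, which brings the 24-hour report. Transaminase elevation is named in Section 2.3 as afatinib's commonest liver effect, so a marked rise without another cause would probably be judged drug-related; if it is grade ≥ 3, the pause rule applies. All of this stands, and it rules out a stronger reading that a reader might infer: that these patients could go unmonitored for about 28 days. That would require an investigator to see a rise of 10 to 15 × ULN and order nothing.

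Even so, these duties do not replace the alert. Most depend on the investigator's judgement of relevance, seriousness or relatedness. A non-serious AE goes to the sponsor within 24 hours only if it bears on a reported SAE or AESI, and interruption for an AE judged unrelated is optional (Section 4.1.4.1.1).

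**Deliberate choice.** AESIs are set at project level, and limiting alerts where enzymes are already raised is a defensible aim. The documents also give no isolated threshold for this group, so 10 × ULN is a proposal borrowed from the normal-baseline limb. Both points stand. But the exclusion for underlying disease already serves that aim, and it does not explain why a patient at 1.1 × ULN without metastases should lose the limb.

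**Modest gain.** The fix mainly adds faster reporting and work-up, because the pause rule already acts on drug-related grade ≥ 3 events. That is fair, and it sets the severity.

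**Conclusion.** The point holds as a limited gap. For patients with AST and/or ALT above ULN at baseline, a marked isolated aminotransferase rise triggers no automatic AESI report, 48-hour evaluation, DILI checklist or at-least-weekly retesting, however high it goes, while bilirubin stays below 2 × ULN. Patients with raised bilirubin alone fall in neither group. What is lost is the automatic alert, not all oversight.

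How many of up to 80 treated patients are affected cannot be derived from the documents and may be zero. The list of AEs that the sponsor always treats as serious, and the DILI checklist itself, are held outside the documents; the list might close part of the gap. CTCAE cut-offs are not given either, so which rises reach grade 3 cannot be confirmed here.

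A reader might also infer that the safety analysis is affected. It is not: Protocol Section 7.3.4 and SAP Sections 7.8.1 and 7.8.2 do not use the alert definition, and no endpoint, hypothesis or stopping rule depends on it. This is a minor improvement to a safety rule.

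**What to change.** In Section 5.3.5.1, make the isolated limb (ALT and/or AST at least 10 × ULN) apply to every patient regardless of baseline. For patients with AST and/or ALT above ULN at baseline, keep the existing exclusion of rises explained by underlying disease. Appendix 10.4 then follows through its cross-reference.

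This also brings patients with raised bilirubin alone under the isolated limb. It does not settle the combined limb for them. Simply assigning them to a group would not either, because a patient with Gilbert's syndrome entering at 2 to 4 × ULN already meets the bilirubin half of that limb in both groups.

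The cost is about one line of protocol text and a few more 24-hour AESI reports and work-ups. Some of these will reflect liver metastases, since 10 × ULN is only a doubling for a patient who enters at 5 × ULN. The retained exclusion limits them, at the price of one investigator judgement that the combined limb already requires.

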4.1.4.1.1 Dose reduction for afatinib

Treatment related AEs will be managed by treatment interruptions and subsequent dose reductions of afatinib according to the schedule described in [Table 4.1.4.1.1: 1](#). Dose reductions will apply to individual patients only. Once the dose has been reduced, it cannot be increased later.

To prevent the development of more severe adverse events, treatment related diarrhoea, nausea and vomiting or rash should be managed early and proactive as described in [Section 4.2](#).

Table 4.1.4.1.1: 1 Dose reduction scheme for afatinib

AE Type and CTCAE Grade	Action	Dose reduction scheme
Events related to study drug: 
 • Diarrhoea Grade 2 persisting for 2 or more consecutive days (48 hours) despite adequate anti-diarrhoeal medication/hydration • Reduced renal function caused by dehydration secondary to diarrhea to Grade 2 as measured by serum creatinine, proteinuria or decrease in glomerular filtration rate of more than 50% from baseline • Any drug related AE Grade ≥ 3 	Pause treatment until patient has recovered to Grade ≤ 1 or baseline ¹ . Resume treatment at reduced dose according to schedule opposite. If patient has not recovered to Grade ≤ 1 or baseline ¹ within 14 days study treatment must be permanently discontinued ² .	If patient was receiving 40 mg, resume treatment at a dose of 30 mg. If patient was receiving 30 mg, resume treatment at a dose of 20 mg. If patient was receiving 20 mg, discontinue afatinib.
Acute onset and/or unexplained worsening of pulmonary systems (dyspnoea, cough, fever)	Pause afatinib while clinical assessment to exclude ILD is completed.	If ILD is ruled out as a cause of symptoms, grade symptoms and relatedness and report as AEs. If AEs are not related, resume afatinib at current dose. If AEs are drug related, follow directions in row above. If ILD is confirmed, discontinue afatinib

¹ Baseline is defined as the CTCAE Grade at the start of treatment

² In the event that the patient is deriving obvious clinical benefit according to the investigator's judgement, further treatment with afatinib will be decided in agreement between BI Clinical Monitor and the investigator.

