In the event of any unrelated adverse events, the investigator may choose to interrupt the medication for up to 14 days, but no dose reduction should occur. If the medication is interrupted for more than 14 days, the decision to continue with afatinib will be made by the BI clinical monitor in agreement with the investigator.

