4.2.3.4 Management of interstitial lung disease (ILD) and keratitis

Careful assessment of all patients with an acute onset and/or unexplained worsening of pulmonary symptoms (dyspnoea, cough, fever) should be performed to exclude interstitial lung disease (ILD). Study drugs should be interrupted pending investigation of these symptoms. If interstitial lung disease is diagnosed, study drug must be permanently discontinued and appropriate treatment instituted as necessary.

Patients who present with symptoms of keratitis, such as acute or worsening eye inflammation, lacrimation, light sensitivity, blurred vision, eye pain and/or red eye should be referred promptly to an ophthalmic specialist. If a diagnosis of ulcerative keratitis is confirmed, treatment with afatinib should be interrupted or discontinued. If keratitis is diagnosed, the benefits and risks of continuing treatment with afatinib should be carefully considered. Afatinib should be used with caution in patients with a history of keratitis, ulcerative keratitis or severe dry eye. Contact lens use is a risk factor for keratitis and ulceration.

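### At a hepatic-injury alert the supplied text requires no hold of afatinib unless the event is judged drug-related and Grade ≥3, whereas suspected ILD is paused before its cause is known

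*Protocol*

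**What the plan says.** **The liver.** Protocol 5.3.5.1 defines an alert by transaminase and bilirubin thresholds and gives its consequence: "These lab findings constitute a hepatic injury alert and the patients showing these lab abnormalities need to be followed up according to the" DILI checklist. Section 10.4.2 sets out the work-up: confirm on the initial sample if possible, evaluate and retest within 48 hours, image within 48 hours if the second sample confirms, complete the checklist if imaging does not explain the result, and then test at least weekly. Neither section mentions holding, reducing or stopping afatinib. Section 4.2.3, on managing expected adverse events, has no hepatic entry.

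**The general dose rules (4.1.4.1.1).** The only mandatory pause that could reach a liver event has the trigger "Any drug related AE Grade ≥ 3". After recovery the instruction is "Resume treatment at reduced dose according to schedule opposite". For events judged unrelated, "the investigator may choose to interrupt the medication for up to 14 days".

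**The comparators.** For suspected ILD the dose table says "Pause afatinib while clinical assessment to exclude ILD is completed", and 4.2.3.4 agrees: "Study drugs should be interrupted pending investigation of these symptoms". ILD is also a named withdrawal reason in 3.3.4.1; hepatic injury is not. For the eye, "If a diagnosis of ulcerative keratitis is confirmed, treatment with afatinib should be interrupted or discontinued".

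**The concern.** Section 2.3 picks out two rare risks for early detection, ILD and drug-induced liver injury, and reports hepatic failure, some of it fatal, in under 1% of patients given afatinib. The two are then handled differently at the moment of suspicion. For ILD, exposure stops first and the cause is sorted out afterwards. For the liver, whether exposure stops depends on a causality judgement and a grade, and the investigations that would inform that judgement may still be under way. The protocol gives no reason for the difference.

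At stake is continued daily dosing of a patient whose liver is being investigated for injury. Sites would also differ, because the hold depends on how quickly, and in which direction, each investigator attributes the event.

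**Working it through.** There is no plan figure to reproduce. The check sets the rules side by side and then does two short calculations.

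**1. What happens at an alert, case by case**

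| Situation | Instruction in the supplied text |
|---|---|
| Judged drug-related, Grade ≥3 | Mandatory pause, with no wait for imaging or checklist; reduced dose on recovery; stop if not recovered in 14 days, with a clinical-benefit exception (Table 4.1.4.1.1:1) |
| Judged unrelated | Interruption optional, up to 14 days (4.1.4.1.1) |
| Not yet attributed | No rule |
| Drug-related, below Grade 3 | No rule; the table's Grade 2 triggers are diarrhoea and renal function |
| Suspected ILD, for comparison | Pause during assessment; relatedness is judged after ILD is ruled out |

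Withdrawal for an adverse event under 3.3.4.1, criterion 3, is available in every row but is discretionary.

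**2. Size of the below-Grade-3 group**

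The CTCAE limits are not in the documents, so this is an assumption shown as a range. Suppose Grade 3 for AST/ALT starts above k × ULN and bilirubin is also below Grade 3. A combined alert then escapes the mandatory pause between its AST/ALT threshold and k. The threshold in 5.3.5.1 is 3-fold with normal baseline liver tests and 5-fold with raised AST/ALT at baseline.

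| k | Normal baseline | Raised baseline |
|---|---|---|
| 3 | essentially none | none |
| 5 | 3- to 5-fold | essentially none |
| 10 | 3- to 10-fold | 5- to 10-fold |

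The group could be almost empty or substantial. The unrelated and unattributed cases do not depend on k.

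**3. When the checklist starts**

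- Section 5.3.5.1 attaches the checklist to the alert itself.
- Section 10.4.2 requires it only after a second sample confirms the alert and imaging has not identified the cause.

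These conflict. Under 10.4.2 alone, with both limits fully used and no pause triggered or chosen: 48 + 48 = 96 hours; 96 / 24 = 4 daily doses; 4 × 40 mg = 160 mg, plus laboratory time. Under 5.3.5.1 this delay does not arise.

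**The case against.** The strongest case is that the gap is narrow and may not exist in practice.

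- **Attribution is quick.** Section 5.3.6 requires an adverse event of special interest to reach the sponsor within 24 hours. It asks for the action taken with the drug and expects a causality judgement. Course visits also pair safety laboratory tests with dose assessment. This shortens the unattributed window. It does not close it, because the section neither says the first judgement is final nor prescribes an action. An early judgement of unrelated, made before the repeat sample and imaging, removes any mandatory pause.
- **The threshold for relatedness is low.** Under 5.3.5.1 it is enough that "a causal relationship between a medicinal product and an occurrence is suspected", and transaminase elevation is a known effect of afatinib (2.3). An unexplained alert at Grade ≥3 should therefore usually be paused. This stands. What is left is the unrelated, unattributed and below-Grade-3 cases.
- **The hold may be written elsewhere.** The checklist, Investigator's Brochure and product label were not supplied. This also stands. Section 10.4.2 describes the checklist only as history and tests, but 5.3.5.1 refers to procedures in it, so a hold rule there cannot be excluded.
- **Numbers are small.** At most 80 patients are treated. If the under-1% rate of hepatic failure applied here, fewer than 0.01 × 80 = 0.8 cases would be expected. That limits the size of the problem but is no reason for leaving the dosing instruction unstated.

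**Conclusion.** The point holds in this form: on the supplied text, afatinib must be held at a hepatic-injury alert only when the event is judged drug-related and Grade ≥3. In the other cases dosing may continue through the work-up, while the comparable lung risk is paused on suspicion. This is a patient-safety inconsistency worth correcting. It affects few patients but could be serious for each. Confidence is medium, because the checklist is unseen and neither the alert rate nor the grade limits are given.

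A reader might infer three stronger things that the documents do not support:

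- **That liver events have no mandatory pause at all.** They do once they are drug-related and Grade ≥3.
- **That the plan builds in 96 hours of dosing before the checklist.** That follows only from 10.4.2 read alone, against 5.3.5.1.
- **That afatinib must never be restarted after an unexplained combined transaminase and bilirubin alert.** The existing row does return a recovered patient at a lower dose, but the only support in the documents for a ban is analogy with ILD. It is a question for the sponsor's safety group.

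**What to change.** Add a hepatic-injury row to Table 4.1.4.1.1:1, built like the ILD row:

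1. Pause afatinib at the alert while the 10.4.2 work-up is done.
2. If the alert is not reproduced, or another cause is established, resume at the current dose on the investigator's judgement. The existing 14-day rule for unrelated events applies.
3. If the event is drug-related, or no other cause is found, follow the existing drug-related row whatever the grade.

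Align 10.4.2 with 5.3.5.1 so that the checklist starts no later than confirmation of the alert, in parallel with imaging. Name one location for it (5.3.5.1 says the RDC system, 10.4.2 the ISF). If the checklist already contains a pause rule, copy that rule into the table instead.

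**Cost.** One table row and one appendix edit; in practice, a short interruption in the few patients with an alert. The pause does not move scans, because Protocol 10.5 keeps tumour assessment on its original schedule. Sample size and analysis methods are unchanged.

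Step 3 could add some discontinuations among below-Grade-3 alerts that do not recover in 14 days. A permanent-stop rule, if the sponsor chose one, would add more. SAP 7.4 ignores assessments later than 30 days after end of treatment and, under its second rule, needs a non-progression scan on or after day 168. A patient stopping before day 168 − 30 = 138 cannot meet that rule. The third rule reaches back to day 154 − 30 = 124 only if its later progression scan is exempt from the 30-day limit. Each added failure lowers PFS6 by 100/70 = 1.4 percentage points at full accrual, or 100/25 = 4.0 points in Stage 1. That cost should be weighed before a permanent-stop rule is adopted; it is not a reason to omit the pause.
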